**Abdominal Muscle Strength Evaluation:**

Abdominal muscle strength will be evaluated using the manometer to sternum method. This method measures the amount of pressure on the sternum when the subject is in a sit-up position (back 20cm off the table both hips at a 30° angle and both feet secured down), and then pressure is exerted on the manometer by the observer to the maximum the subject can sustain.

**Circumference Evaluation:**

Abdominal circumference measurements is a tool used to measure abdominal fat by wrapping a tape measurer around the waist. Measurements may be taken at baseline, pre-treatment 5, and at the 30 and 90 day follow up visits.

**Temperature Monitoring:**

An infrared thermometer may be used for temperature monitoring to measure temperature on the skin before, during, and after treatment.

**Physician and Subject Questionnaire:**

The Global Aesthetic Improvement Scale (GAIS) ranging from “worse” to “very much improved” will be used to judge the improvement as seen by the subject and Investigator.

Global Aesthetic Improvement Scale Assessment	
Rating	Description
1	Very Much Improved- Optimal cosmetic result in this subject
2	Much Improved- Marked improvement in appearance form the initial condition, but not completely optimal for this subject.
3	Improved- Obvious improvement in appearance from initial condition, but a re-treatment is indicated.
4	No Change- The appearance is essentially the same as the original condition.
5	Worse- The appearance is worse than the original condition.

**Subject Questionnaire:**

The subject will be asked their level of satisfaction using a 6-point Likert scale that ranges from “extremely satisfied” to “extremely unsatisfied.”

Subject Satisfaction	
Rating	Description
6	Extremely Satisfied
5	Satisfied
4	Slightly Satisfied
3	Slightly Unsatisfied
2	Dissatisfied
1	Extremely Unsatisfied

## **2.14 Adverse Event Recording**

All data captured must be supported by the Investigator's timely assessment and documentation of the adverse event in the case report forms or source documents. All documented adverse events will be reviewed by the Sponsor or designee to determine whether the adverse event meets regulatory reporting requirements and to ensure timely adverse event reporting to meet local and global regulatory requirements. All adverse events must be followed until their resolution.

### **Adverse Events Pertaining to the Brera/Med 400 Device:**

Mild discomfort during treatment may be experienced by the subject. Typically, the discomfort is temporary and localized within the treatment area. Mild edema (swelling), pain/soreness, cramping, and erythema (redness) may occur.

Other possible anticipated side effects may include; numbness, muscle twitching (which may last days), skin burns, bleeding, scarring, crusting, bruising, infection, itching, prolonged edema (swelling) and erythema (redness), hardness, and nodules. Loss of hair pigment may also occur within and adjacent to the treatment area.

### **Adverse Events Pertaining to the Surgical Marker:**

Using surgical marker has minimal risks and may produce effects on the body such as redness or a rash. Markings may remain visible for a few days or may be removed with alcohol.

### **Other Cautions:**

Incomplete response or no response may occur since some subjects may not respond to treatment.

## **2.15 Statistical Analysis**

### **2.15.1 Hypothesis**

For this study to be considered a success, the side effect profile is acceptable to the Physician as it relates to this type of treatment.

For the additional assessments to be considered a success, the following must be true:

- Pre-treatment images when compared to post treatment (90 day) images will be  $\geq 80\%$

- In cases where the subject's improvement is being graded on a scale, such as the GAIS scale, we will test the statistical significance of our results against a hypothetical population that would have no change (average score of 4).
- Subject treatment and clinician usability questionnaires are collected.
- The side effect profile (adverse events) and the average pain score is acceptable to the Physician as it relates to the type of treatment.

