### **1.2 Objectives**

1. Primary Objective:
  - Evaluation of adverse events and side effects throughout the study.
2. Optional Assessments:
  - Photographic evaluation with correct identification of pre-treatment 2D images when compared to the 30 and 90 day follow up images performed by three independent reviewers.
  - Abdominal circumference reduction evaluated using a tape measurement.
  - Principle Investigator assessment using the Global Aesthetic Improvement Scale Abdominal fat reduction evaluated using an ultrasound device
  - Principle Investigator assessment using the Global Aesthetic Improvement Scale (PGAIS) at the 30 and 90 day follow up visit.
  - Subject Questionnaire(s)
    - The Global Aesthetic Improvement Scale (SGAIS) at the 30 and 90 day follow up visit.
    - Subject satisfaction at the 30 and 90 day follow up visit.
    - Psychometric Questionnaire (muscle firmness, hardness, self-image, and well-being)
    - Subject Treatment Questionnaire
  - Collection of 3D Photography
  - Objective measurement of abdominal muscle strength.
  - Temperature monitoring.
3. Additional Safety Objectives:
  - Collection of Treatment Discomfort/Pain Evaluation

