#### 2.15.2 Sample Size Rationale

Based on the need for data collected from this study, it was determined that a total of 20 subjects will be required, including departures.

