## 2.15.6 Analysis of Safety Variables

Safety will be assessed through the degree of pain/discomfort related to the procedure (universal pain scale) and the collection of Adverse Events throughout the course of the study. For each treatment group these variables will be summarized. The summaries will include the number and percent of patients for each outcome. No statistical comparisons will be performed for any of these variables.

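### The primary safety objective succeeds on a physician's judgement of acceptability, and no adverse-event result is prespecified to mean failure

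*Combined protocol and SAP*

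**What the plan says.** Section 1.2 gives the primary objective as "Evaluation of adverse events and side effects throughout the study". It attaches no endpoint or rate.

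Section 2.15.1 (Hypothesis) states the only success rule for that objective: "For this study to be considered a success, the side effect profile is acceptable to the Physician". The sentence goes on to qualify this by the kind of treatment. The section then lists success conditions for the additional assessments, and the same judgement appears again there, extended to pain: "The side effect profile (adverse events) and the average pain score is acceptable to the Physician as it relates to the type of treatment". No pain cut-off is given.

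Section 2.15.6 makes the safety analysis descriptive. Adverse events and pain are summarized for each treatment group: "The summaries will include the number and percent of patients for each outcome". It adds: "No statistical comparisons will be performed for any of these variables".

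On size, Section 2.15.2 says "it was determined that a total of 20 subjects will be required, including departures", while Section 2.1 allows enrolment of up to 30. Section 2.2 describes the design as open label at a single center.

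**The concern.** A success criterion is useful if a reader can say beforehand which results would meet it and which would not. Here the reader cannot. The protocol leaves the meaning of acceptable, and the question of who decides and when, to be settled later. Nothing in the text stops them being settled with the results in view, and Section 2.15.3 allows interim results to be collected and reported.

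This matters more because safety is the primary objective. Section 3.3 describes the device as uncleared with limited safety data, and Section 24.0 lists no earlier protocol for it. A report that the study met its primary criterion would be read as evidence on safety. As written, it would mean that an unspecified physician was content with what was observed, by an unstated standard.

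**Working it through.** **1. Is a failure criterion written anywhere?** The places where one could stand are these.

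| Section | What it supplies | Is it a success or failure criterion? |
|---|---|---|
| 1.2 | Primary objective | No endpoint or threshold |
| 2.14 | Anticipated effects, from mild redness and soreness to burns, infection, scarring and nodules | A list without rates |
| 2.15.1 | Physician acceptability | The only rule; acceptable is undefined |
| 2.15.6 | Number and percent per outcome | Description only |
| 3.2 | Risks said to match those of similar non-ablative radiofrequency treatment | A qualitative reference without rates |
| 14.0 | Five relationship grades, three severity grades, a definition of serious events | Graded, but not linked to success |
| 22.0 | The investigator may stop the study for safety, in collaboration with the sponsor | No criteria, and not a success rule |

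No section provides an event type, maximum rate, severity level, comparator rate or confidence bound.

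**2. Comparison within Section 2.15.1.** The photographic assessment has a numerical cut-off: "Pre-treatment images when compared to post treatment (90 day) images will be" at least 80%. Graded scales such as the GAIS have a reference value, a mean score of 4 for no change. Both are additional assessments. The primary objective has neither a cut-off nor a reference value.

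**3. Who judges.** Section 2.15.1 says only that it is the physician. Section 14.0 has the investigator and/or study staff assess relationship to the device. Section 3.2 acknowledges bias and requires blinded outside evaluators for photographs if these are a primary objective. It has no counterpart for safety.

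**4. Operating characteristics.** The probability of declaring success at a given true event rate requires a mapping from counts to decisions. The written rule has none, so neither error rate can be computed. The sample size cannot be reproduced from a safety target either, because Section 2.15.2 gives no rate, margin, alpha or power.

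For contrast, take a purely illustrative rule: success if at most 1 subject has a defined device-related event. The cut-off and the true rates p are assumptions, not proposals.

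P(success) = (1 − p)^n + n·p·(1 − p)^(n − 1)

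- n = 20, p = 5%: 0.3585 + 0.3774 = 0.74
- n = 20, p = 10%: 0.1216 + 0.2702 = 0.39
- n = 20, p = 20%: 0.0115 + 0.0576 = 0.07
- n = 30, same rates: 0.55, 0.18 and 0.01

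Any rule of this kind has error rates that can be examined before the trial starts.

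**5. Context: what a low count can show.** Assume that all n subjects are treated and that none has the event. The exact (Clopper-Pearson) two-sided 95% upper limit is 1 − 0.025^(1/n).

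- n = 20 (Section 2.15.2): 1 − 0.8316 = 16.8%
- n = 30 (Section 2.1): 1 − 0.8843 = 11.6%

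An event with a true rate of 5% would be missed altogether with probability 0.95^20 = 36% at n = 20, and 0.95^30 = 21% at n = 30.

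**The case against.** The strongest defence is that this is a small, open-label, single-center study with a descriptive safety analysis, where an experienced clinician's judgement is a reasonable summary. That opinion concerns observed data, namely the side effect profile tabulated under Section 2.15.6. It also has a reference class, since the rule is qualified by the type of treatment, and Sections 2.14 and 3.2 describe what is expected of such treatment. A descriptive study needs no threshold.

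Much of this stands, and it rules out several stronger readings that a reader might infer:

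- That no adverse-event result can fail the rule. Read literally, it fails if the physician finds the profile unacceptable. What is missing is any result specified in advance to mean failure.
- That the rule is unconnected to the data, or that success says nothing about safety. The observed profile is what is assessed, and a physician's opinion of it carries some information. The missing element is a cut-off.
- That the person deciding is the unblinded treating investigator, acting after the results. This is plausible in an open-label, single-center study, but the documents do not say so. Their silence is part of the problem.
- That Section 2.15.6 excludes confidence intervals. Its sentence on statistical comparisons follows one about summaries by treatment group and most naturally rules out between-group tests.
- That the 16.8% and 11.6% limits measure the fault in the rule. They would be the same under any rule and describe only the precision of a small sample.

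The defence does not remove the main point. Section 2.15.1 does not present the study as purely descriptive. It declares a condition for success under the title of a hypothesis, and the expected-effects list gives no rates and is too broad to serve as a standard.

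**Conclusion.** The concern holds in this form: the only success rule for the primary safety objective is a physician's judgement of acceptability, with no adverse-event result prespecified to mean failure and no statement of who judges, when, or whether independently. Almost any profile could be called a success once the data are seen. This is a stated rule that is inadequately specified, and it should be changed.

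The fault has no numerical size, because the written rule has no error rate to compute. The zero-event limits of 16.8% (n = 20) and 11.6% (n = 30) are context for reporting and assume that every planned subject is treated. The conclusion does not depend on which of the two enrolment figures applies, although 20 and 30 should be reconciled.

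**What to change.** Amend Section 2.15.1 to define the primary safety measure from data that Section 14.0 already collects: the proportion of treated subjects (the safety population of Section 2.15.3) with at least one device-related event, graded possible or higher, of moderate or severe intensity. Report it with an exact 95% CI, together with the number of subjects with device-related serious events. Then choose one of two courses.

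- **(a) Keep a success criterion.** Compare the proportion with a limit that the sponsor sets and justifies before any data, including interim data, are reviewed. State whether the point estimate or the upper confidence limit is compared. This choice can decide the outcome: with zero events in 20 subjects, any limit above zero but below 16.8% is met by the point estimate and missed by the upper limit.
- **(b) Make the objective descriptive.** Say so, report the exact CIs, and remove the success wording for safety.

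Under either course, keep the physician's view as commentary and say whose view it is.

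No new data collection is needed. The rule stands in the protocol itself, so Section 21.0 requires a formal amendment with written IRB approval. Under (a) the study can fail its primary criterion. Under either course the reported intervals will be wide.

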#### 2.15.2 Sample Size Rationale

Based on the need for data collected from this study, it was determined that a total of 20 subjects will be required, including departures.

#### 2.15.3 Patient Populations

Interim results may be collected and reported. All data will be analyzed at the end of the study. The primary analysis will be performed by the intention-to-treat approach. Everyone who begins the treatment is part of the study whether he or she completes the study or not. Additional per-protocol analysis may also be performed on subjects assigned to Group A who complete the entire clinical trial according to the protocol. The most appropriate method of handling missing values will be chosen based on the individual trial goals, endpoints and context.

The analysis of demographic, medical history, and efficacy variables will be based on all patients who are randomized and receive at least one treatment. The analysis of safety data will be based on all patients who receive at least one treatment, and have at least some safety data.

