## 2.0 PROTOCOL

### **2.1 Protocol Methodology and Analysis**

Methodology:

Subjects are to be enrolled in this clinical study if they are a healthy male or female 18 years of age or older. Up to 30 subjects will be enrolled at 1 study center. Subjects will be enrolled into 2

groups, Group A and Group B. Subjects will be enrolled in Group A if they present with abdominal fat and are able to be present for all visits as outlined in “Schedule of Visits and Procedures – Group A”. Subjects will enroll in Group B for training and experience purposes only and will follow the visit schedule as outlined in “Schedule of Visits and Procedures – Group B”. Randomization will not be required as each subject will be assigned to a group depending on the purpose of their treatment(s). All subjects will attend a screening/pretreatment visit which may be performed on the same day as the treatment visit.

Subjects in Group A will receive up to 8 treatments with the Brera/Med 400 device on their abdomen or flanks. Subjects may receive a phone call 1 week (1-7 days) after each treatment to record side effects. Subjects will return for follow up visits at 30 and 90 days post last treatment for efficacy and side effects assessments.

Subjects in Group B may receive up to 8 treatments with the Brera/Med 400 device on their abdomen and/or flanks. Subjects may receive a phone call 1 week (1-7 days) after each treatment to record side effects. Subjects may be asked return for follow up visits at 30 and 90 days post last treatment for efficacy and side effects assessments.

An unscheduled visit or phone call may be performed at any time during the study at the request of the subject or as deemed necessary by the site Investigator.

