### **2.2 Protocol Study Design**

This is a prospective, open label, single center clinical study to collect safety and efficacy data on the Brera/Med 400 device.

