#### Inclusion Criteria:

- A healthy male or female 18 years of age or older.
- Agrees to be treated with the Brera/Med 400 device.
- Understands and accepts obligation not to receive any other procedures on the treatment area through the length of the study.
- Understands and accepts the obligation and is logistically able to be present for all visits.
- Is willing to comply with all requirements of the study and sign the informed consent document.

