**CONCLUSION:**

This device is determined to be a non-significant risk study and will be using a device not cleared for use by the FDA.

Patient population to be enrolled in this clinical study:

Total anticipated population: 30 Subjects

Age Range: 18 years of age or older

Gender: Male or Female

Condition: Muscle stimulation and abdominal fat.

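### The efficacy set is limited to randomized patients in a study that randomizes no one, and the plan does not say whether Group B training subjects count towards the photographic and GAIS criteria

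*Combined protocol and SAP*

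**What the plan says.** Section 2.15.3 gives the only definition of an efficacy set. Demographics, medical history and "efficacy variables will be based on all patients who are randomized and receive at least one treatment". The same section names intention-to-treat as the primary approach and counts any subject who starts treatment, in either group. Only a per-protocol analysis, which is optional, is limited to Group A. The safety set is defined by treatment and available safety data, with no mention of randomization.

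Section 2.1 states: "Randomization will not be required as each subject will be assigned to a group depending on the purpose of their treatment(s". Section 2.2 adds: "This is a prospective, open label, single center clinical study to collect safety and efficacy data". No allocation procedure appears anywhere.

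The two groups enter on different terms. Section 2.1 says "Subjects will be enrolled in Group A if they present with abdominal fat and are able to be present for all visits", whereas "Subjects will enroll in Group B for training and experience purposes only". The inclusion list in section 2.3 opens with "A healthy male or female 18 years of age or older", and no inclusion or exclusion criterion requires abdominal fat. In Group B the 30- and 90-day visits are optional, as are ultrasound, circumference, strength, GAIS and satisfaction (section 2.12).

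Section 2.15.1 sets a photographic criterion of at least 80% at 90 days and a test of GAIS against a score of 4, without naming a group. Section 2.15.5 summarizes change from baseline and tests it separately for each treatment group, then compares the groups at visit 11 with a two-sided threshold of 0.05.

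**The concern.** A set that requires randomization has no members when no one is randomized, so whoever analyses the data must replace the rule. Two replacements are available: all treated subjects, or treated Group A subjects. The plan does not choose between them. The study is open label and section 2.15.3 allows interim results to be reported, so the choice could be made after results are known.

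The choice matters because the groups were formed for different purposes. Group B exists to give operators experience, its subjects need not have the condition being treated, and whether they are measured after treatment is discretionary. If they count towards a criterion that names no group, the result depends on how many of them were enrolled and how many happened to return. If they serve as the second arm of a significance test, the test compares two groups given the same device on different visit schedules and separated by purpose of enrolment. It has no clear interpretation as a treatment effect.

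**Working it through.** **Set membership.** The rule in 2.15.3 is: randomized AND treated at least once. Section 2.1 puts the number randomized at zero, so the literal set has 0 members. Deleting the word *randomized* leaves every treated subject in both groups, up to the 30 in section 2.1. Restricting to Group A leaves treated Group A subjects only.

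**Where Group B can affect a result if it is admitted.**
- Mean change from baseline (2.15.5): summarized and tested by group, so Group A's figure stands alone.
- Photographic criterion and GAIS against 4 (2.15.1): no group named, so pooling is open.
- Comparison at visit 11 (2.15.5): uses Group B directly.
- Safety (2.15.3, 2.15.6): the set has no randomization term, so it is unaffected.

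**Size for the photographic criterion.** There is no plan figure to reproduce: no A/B split is stated, and the total of 20 in section 2.15.2 comes without an effect size, standard deviation, power or dropout rate. The following is therefore an illustration. Let f be Group A's share of the photograph pairs, and let p be the correct-identification rate in Group A. Assume that Group B pairs are identified at the chance rate of 50%.

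Pooled rate = f × p + (1 − f) × 0.5

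Setting this to 0.80 gives p = (0.80 − 0.5 × (1 − f)) / f.

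| Assumed split (A+B) | f | Group A rate needed |
|---|---|---|
| 25+5 | 0.833 | (0.80 − 0.083) / 0.833 = 86% |
| 20+10 | 0.667 | (0.80 − 0.167) / 0.667 = 95% |
| 15+15 | 0.500 | (0.80 − 0.250) / 0.500 = 110%, not attainable |
| 15+5 (total of 20) | 0.750 | (0.80 − 0.125) / 0.750 = 90% |

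With Group A alone the requirement is 80%. The table assumes that every Group B subject supplies a 90-day pair. Because that visit is optional for them, the true f would be nearer 1 if some do not return, and the effect smaller.

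**GAIS.** If Group B averaged 4 (no change), the pooled distance from 4 would be f times Group A's distance: 0.833 of it at 25+5 and 0.667 at 20+10, under the same assumption that all are scored.

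**The case against.** A reader might infer that Group B dilutes the estimate of fat reduction, by 20% at 20+5 (5/25) or 33% at 20+10 (10/30). The documents do not support this. Section 2.15.5 reports and tests change for each group separately, section 2.15.1 sets no pooled threshold for circumference or ultrasound, and both the split and a Group B change of exactly zero are assumptions. The treatment of subjects without follow-up is also unsettled, since section 2.15.5 both assumes zero change for them and leaves their changes missing.

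A reader might also infer that the efficacy analysis would be empty. Read literally it is, but the intention-to-treat sentence in the same section shows that the likely intent was all treated subjects. The empty set is a drafting error, not a realistic outcome. That likely intent does, however, lead to the reading that admits Group B.

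It is fair to add that nothing says Group B subjects lack abdominal fat. The conclusion of section 3.3 describes the whole anticipated population of 30 with "Condition: Muscle stimulation and abdominal fat". That is a description and not a selection criterion, but it counts against assuming a lean Group B. Muscle strength is also assessed, so a leaner subject is not outside every efficacy target.

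Finally, section 1.2 makes adverse events the primary objective and lists the efficacy measures as optional. This stands, and it limits the severity. Keeping both groups and reporting them apart throughout would be a defensible alternative, but the plan does so only for change scores.

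**Conclusion.** The point holds in a limited form. The definition in 2.15.3 contradicts 2.1 and cannot be applied. Its natural repair admits subjects enrolled for training, without a fat criterion and with discretionary follow-up. The exposure is confined to the two criteria in 2.15.1 that name no group and to the visit 11 comparison in 2.15.5.

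For photographs, the illustration raises what Group A must achieve from 80% to 86% (25+5) or 95% (20+10). These figures rest on assumed splits, a 50% identification rate in Group B, pooling, and 90-day photographs from every Group B subject.

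This should be fixed. It is not critical, because the primary safety objective and its analysis set are unaffected.

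**What to change.** - **2.15.3:** delete *randomized* and define the efficacy set as Group A subjects who receive at least one treatment. Define the demographic and medical-history set as all treated subjects. Keep the safety set as all treated subjects with safety data. Show both by group.
- **2.15.1:** state that the photographic and GAIS criteria are assessed in the Group A efficacy set.
- **2.15.5:** remove the pairwise comparison at visit 11 and its significance rule, which would have no second group once the set is Group A only. Report Group B efficacy data separately and descriptively.
- **2.3:** carry the abdominal-fat condition for Group A over from 2.1. This is tidying, since 2.1 already imposes it.

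The cost is a few sentences across four sections, in an amendment settled before the data are analysed. The downside is that Group B contributes no inferential efficacy data.
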